Radiologic assessment will occur at screening and the end of cycles 6, 12, and 24 (if applicable). Radiologic assessment at other time points will be at the discretion of the treatment team. PROs Measurements and CBA will begin at screening and will occur at the end of every 6 cycles throughout the duration of the study and extension period. If there are any signs of worsening prior to study evaluations, then the Principal Investigator (PI) should complete earlier assessment for evaluation of response.

Therapy will be discontinued if there is evidence of worsening disease or drug related dose-modifying toxicity that requires removal from therapy. Treatment may otherwise continue to the end of the study intervention phase and subsequent extension period provided the subject meets the criteria for starting subsequent cycles and does not meet criteria for removal.

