6.4 Follow-up Phase

All subjects, including those who discontinue protocol therapy early, will be followed at least 30 days following cessation of study drug unless withdrawal of consent occurs.

There will be one scheduled visit 30 days following completion of the trial (after cycle 24 if not continuing on to the extension phase) or cessation of study drug. The following procedures will be performed at the follow-up visit:

- Medical history and Assessment for adverse events
- Concomitant medications
- PE with dermatologic examination (Photograph(s) of new or changing cutaneous lesions, lymphedema, or other)
- Height, weight, and vital signs: temperature, pulse, blood pressure, respiratory rate, oxygen saturation by pulse oximeter
- Performance Status: Karnofsky/Lansky Performance Score.
- Laboratory studies as outlined in section [6.1 Screening Assessments](#)
- Pregnancy testing for all subjects of childbearing potential: serum or urine pregnancy testing
- Collect unused study drug and diary
- If not done within 3 months of the study termination the following needs be to performed:
 - Ophthalmologic exam as outlined in section [6.1 Screening Assessments](#)
 - ECHO as outlined in [6.1 Screening Assessments](#)

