8.3.2 Response Criteria for Overall Response

The primary endpoint of this VATCH sub-protocol is to determine whether the MEK inhibitor trametinib administered once a day on a continuous dosing schedule to subjects with Ras/MAPK pathway driven Vascular Anomalies provides an objective response at the end of cycle 6. Assessment of response is an individualized response criterion based on radiologic assessment, Patient Reported Outcome Measurements (composite score) and Clinical Benefit Assessment. Disease Response is determined by the local institution/investigator and is defined below.

Clinically meaningful response:

A clinically meaningful response includes a substantial response, Intermediate response or stable disease at the timing of protocol assessment.

Assessment of individualized response criteria after 6 cycles for primary endpoint and then every 6 months.

Substantial response:

- Improvement in Radiologic assessment (if applicable) by 20% AND
- Improvement in Global Health PROs by 3T-score points* AND
- Improvement in at least 1 CBA as reported by the clinician AND
- No clinically meaningful worsening in any measure

Intermediate response:

- Improvement in Radiologic assessment (if applicable) by 20% OR
- Improvement in Global Health PROs by 3 T-score points* OR
- Improvement in at least 1 CBA as reported by the clinicians AND
- No clinically meaningful worsening in any measure

Stable disease:

- No clinically meaningful improvement or worsening from screening in
 - Radiologic assessment (if applicable), OR
 - Global Health PROs*, OR
 - CBA as reported by the clinician

Worsening disease:

- Clinically meaningful worsening in
 - Radiologic assessment (if applicable) by 20%, OR
 - Global Health PROs by 3T-score points*, OR
 - CBA as reported by the clinician
 - **Regardless** of any concomitant improvement in other measures.

*Prior review articles have indicated that a change of 2 to 6 T-score points is the minimum important change (MIC) for PROMIS measures. PROMIS leadership recommends 3 T-score points as the MIC^{61,62}.

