9.3 Statistical Analyses Plan

For all the analyses, subjects who received any dose of trametinib will be included in the analyses. The primary efficacy endpoint is objective response (including both response and partial response) at the end of cycle 6 and the primary safety endpoint is toxicity of trametinib. We will use binomial distributions to estimate the response and the toxicity rates with their 95% exact CIs. For the second primary efficacy endpoint of responses at the end of cycles 12 and 24, the response rate will also be calculated with 95% CI. For the secondary endpoint of duration of response, time from initial response to disease progression will be examined, and subjects will be censored at the last adequate disease assessment if no progression occurred by that time. We will use the log-rank tests and/or Cox proportional hazard regression to analyze the endpoint. Should the data suggest the violation of the

proportional hazard assumption, we will consider an alternative method such as accelerated failure time model analysis.

Secondary data analyses will be performed for the secondary outcomes of longitudinal measurements of radiologic assessment, PROMIS Patient Reported Outcome measurements, and Clinical Benefit Assessments, taken at screening, and at the end of cycles 6, 12, 18, and 24. The longitudinal data will be analyzed separately at each follow-up time point and together longitudinally. The paired t-test will be used to look at changes in these measures from pre-treatment levels to the post-treatment level (follow-up at cycle 3) to evaluate the treatment's short-term effects. Mixed effects models will be used for longitudinal analysis to evaluate changes in these measures over time. Should the data suggest the distributions of the measurements deviate from normal distributions, we will consider nonparametric alternatives such as Wilcoxon signed rank test or transformation. Relationships between PROMIS measures and other variables such as pain will be investigated using correlation analysis. Lastly, exploratory analyses will be performed for biomarker measures such as cell-free DNA. Descriptive statistics will be generated to summarize data.

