10.4 Criteria for Removal from Protocol Therapy and Off Study Criteria

10.4.1 Criteria for Removal from Protocol Therapy

- a) Intolerable toxicity (leading to treatment interruption >4 weeks)
- b) Worsening disease at any time at the discretion of the investigator
- c) Refusal or withdraw of consent for further protocol therapy by parent/guardian/LAR or subject
- d) Physician determines it is in subject's best interest
- e) Completion of planned therapy
- f) Non-compliance with protocol requirements (e.g., unexcused missing more than one scheduled study visit or missing > 15% of doses of study drug)

Subjects who are off protocol therapy are to be followed (as indicated) until they meet the criteria for Off Study (see below). For subjects who withdrawal due to AE, the medical condition will be tracked for at least a month after discontinuing the study drug or until resolution of the AE.

Follow-up data will be required until one of the following off study criteria is met.

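### Per-visit analyses of imaging, PROMIS and CBA change after cycle 6 are selected toward benefit, because worsening on these measures can end measurement and 9.3 gives the mixed model no precedence

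*Protocol*

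**What the plan says.** Section 9.3 treats imaging, PROMIS and CBA as longitudinal secondary outcomes "taken at screening, and at the end of cycles 6, 12, 18, and 24". It then states: "The longitudinal data will be analyzed separately at each follow-up time point and together longitudinally". For the joint part, "Mixed effects models will be used for longitudinal analysis to evaluate changes in these measures over time". A paired t-test is named, but for a comparison of pre-treatment values with a cycle 3 follow-up; Wilcoxon or a transformation is the fallback for non-normality. The section opens with "For all the analyses, subjects who received any dose of trametinib will be included in the analyses".

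Removal for worsening is described in three places. The experimental design schema says "Therapy will be discontinued if there is evidence of worsening disease or drug related dose-modifying toxicity that requires removal from therapy". Section 10.4.1 lists "Worsening disease at any time at the discretion of the investigator". Section 4.6 leaves stopping for progressive disease to the physician.

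In 8.3.2 any one component defines worsening disease, whatever the others show: 20% on imaging, 3 T-score points on Global Health, or the CBA. The 3-point size is the one also used for improvement (intermediate response includes "Global Health PROs by 3 T-score points* OR").

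Off therapy, 6.4 provides that "There will be one scheduled visit 30 days following completion of the trial" or after drug cessation. Its procedure list has no PRO, CBA or imaging. Section 8.1 adds one visit, as soon as possible, for subjects who leave the study early, with the end-of-treatment assessments.

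**The concern.** A change-from-screening analysis done on its own at cycle 12, 18 or 24 needs a value at that visit. Whether a subject has one depends partly on the outcome being analysed, since a bad result at cycle 6 can end therapy and with it the scheduled efficacy measurements. Those left are enriched for subjects whose earlier readings were good, partly by chance. The separate analysis then describes subjects who had not been removed for worsening, while the secondary objective concerns change in the treated population.

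The trial has one arm, so no control group shares or exposes the distortion. Section 8.2 itself describes a course that fluctuates for reasons other than treatment, the setting in which chance falls would trigger removal. At stake is how secondary change results after cycle 6 are reported.

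**Working it through.** **Which subjects have a value.** Cycle 6 comes before any removal based on a scheduled post-baseline assessment. After removal, the documents schedule at most the early-discontinuation visit and the 30-day visit; neither is timed to cycle 12, 18 or 24. The 1-year period in 13.2 concerns SAE reporting. A removed subject therefore has no scheduled value at the later visits, and a separate analysis there cannot contain all dosed subjects.

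**Size.** The protocol gives no power or effect figure for these analyses, so there is nothing to reproduce. The illustration covers PROMIS only.

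Inputs from the protocol: T-score SD 10 (8.2.2), a 3-point fall as worsening (8.3.2), 39 subjects (9.1). Assumptions: no true change, a stable course, normal scores, equal correlation r between visits of 0.6 to 0.9, removal driven by the PRO component alone, and a share p of those who worsen being removed (1, 0.5 or 0.25, to cover the discretionary wording).

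Change from screening has SD s = √(2 × 10² × (1 − r)). Changes at cycles 6 and 12 share the screening value, so their covariance is 10² × (1 − r) and their correlation 0.5. With a = 3/s:

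- share still measured at cycle 12: K = 1 − p × (1 − Φ(a))
- apparent mean gain at cycle 12: G = 0.5 × s × φ(a) × p / K

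For r = 0.7: s = 7.75, a = 0.387, φ(a) = 0.3701, Φ(a) = 0.6507.

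- p = 1: K = 0.651 (about 25 of 39); G = 0.5 × 7.75 × 0.3701 / 0.651 = 2.20.
- p = 0.5: K = 1 − 0.5 × 0.3493 = 0.825; G = 0.5 × 7.75 × 0.3701 × 0.5 / 0.825 = 0.87.

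Cycle 24 and the error rates come from simulation, which agrees with the formula at cycle 12. The last two columns apply only if a two-sided 5% paired t-test were used with 39 starters; the nominal rate of false improvement is 2.5%.

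| Share of worsened subjects removed | Still measured, cycle 12 | Gain, cycle 12 | Gain, cycle 24 | False improvement, cycle 12 | False improvement, cycle 24 |
|---|---|---|---|---|---|
| All | 63–75% | +1.0 to +2.7 | +1.9 to +5.0 | 21–33% | 52–65% |
| Half | 82–87% | +0.4 to +1.0 | +1.0 to +2.7 | 7–10% | 23–32% |
| A quarter | 91–94% | +0.2 to +0.5 | +0.5 to +1.3 | 4–5% | 10–13% |

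At cycle 6 the simulated rate is 2.3% to 2.8%, which is nominal. If correlation instead decays with time (first-order autoregressive, r = 0.7 to 0.9), the full-removal gain is larger: +1.8 to +3.8 at cycle 12 and +4.7 to +7.8 at cycle 24.

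**The alternative already in 9.3.** A mixed model on the same data, keeping the visit at which worsening was recorded, gave mean changes of −0.04 to +0.04 points with the covariance known. With an unstructured covariance it gave −0.17 to +0.15 at cycle 12.

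**The case against.** The strongest reply is that 9.3 already plans the mixed model for change over time, ties the paired t-test to cycle 3, and never says that per-visit results at cycles 12 to 24 will be tested. On this view they may be descriptive summaries, with precedence left to an analysis plan that is not shown. Much of this stands. A reader might infer that 9.3 prescribes a paired t-test at each later visit; it does not, so the false-improvement rates above are conditional. What survives is that the separate analyses are stated, the inclusion of all dosed subjects is stated, and the two cannot both hold after removals. The bias in the mean does not depend on a test.

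A reader might also infer that every worsened subject leaves. Only the schema says this flatly; 4.6 and 10.4.1 make it a judgement, and the full-removal row is the upper case. Nor is the 30-day visit the only later contact: 8.1 adds an early-discontinuation visit. The body of Table 8-1 was not available in the text reviewed, so the content of that visit cannot be checked, but it is a single visit.

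Finally, a reader might conclude that an inert drug would be shown to improve all three outcomes. That goes too far. Only PROMIS was simulated, and the result needs a stable course. In progressive disease the same selection would mask decline. Section 8.2.1.1 schedules no imaging at cycle 18.

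**Conclusion.** The point holds for the separate analyses at cycles 12, 18 and 24. Their mean change is selected toward benefit by rules the protocol states, and 9.3 does not say that the mixed model takes precedence. Under the stable-course assumptions, full removal produces at cycle 12 a gain of about a third to nine tenths of the protocol's 3-point important change (0.96/3 to 2.7/3), and at cycle 24 the upper values exceed it. With a quarter removed the cycle 12 effect is small, but it grows by visit. The size rests on an unstated correlation and an unsettled removal rule; the direction does not rest on the correlation chosen. The cycle 6 primary endpoint is untouched by this mechanism, so this is a correction that should be made to secondary analyses and not a threat to the main result.

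**What to change.** In 9.3, name the mixed model already planned as the analysis of record for change after cycle 6. Fit it to all dosed subjects, with screening and every observed value as outcomes (including early-worsening and end-of-treatment assessments) and visit as a categorical factor. Report change from screening at each scheduled visit from this model. Show observed-case changes at cycles 12, 18 and 24 descriptively, without p-values, beside the number removed for worsening before that visit. If normality fails, transform within the model; a per-visit rank test on the remaining subjects would bring the selection back.

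Separately, reconcile the schema, 4.6 and 10.4.1 on removal for worsening, since the size of the bias depends on which applies. This review takes no position on the clinical rule.

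The cost is a few sentences, with no new visits, data or subjects. The downside is that the model assumes missingness at random given the recorded values of that measure. This is only partly met when removal follows another component or clinical judgement, so the bias is reduced but may not be removed fully. Estimates will also tend to look less favourable than observed-case means.

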8 STUDY EVALUATIONS AND MEASUREMENT

8.1 Schedule of Assessments

The schedule of assessments [Table 8-1](#) lists all the assessments to be performed as part of the study, an "X" in the table indicates the visit(s) when they are to be performed.

All data obtained from these assessments must be supported in the subject's source documentation.

Subjects should be seen for all visits/assessments as outlined in the assessment schedule ([Table 8-1](#)) or as close to the designated day/time as possible. Missed or rescheduled visits should not lead to automatic discontinuation. Subjects who prematurely discontinue the study for any reason should be scheduled for a visit as soon as possible, at which time all of the assessments listed for the end of treatment visit will be performed. At this visit, all dispensed investigational product should be reconciled, and the adverse event and concomitant medications recorded on the eCRF.

During the course of the study, test procedures should occur on schedule whenever possible as per allowable visit. For Cycles 1-3, the window is +/- 3 days; for all other cycles, the window is +/- 7 days.

If the COVID-19 or other pandemic limits or prevents on-site study visits, alternative methods of providing continuing care may be implemented. Phone calls or virtual contacts (e.g. teleconsultation), can replace on-site study visits, for the duration of the pandemic until it is safe for the subject to visit the site again.

Table 8-1 Schedule of Assessments

Footnotes:

Day¹: Cycles 1-3: +/- 3 days; Cycles 6-24: +/- 7 days

Laboratory studies²: as outlined in section [6.1 Screening Assessments](#)

Urine or serum pregnancy³: as outlined in section [6.1 Screening Assessments](#)

ECG⁴: repeat during the study if abnormal at screening or as clinically indicated per treating team (not triplicate)

X⁴: repeat during the study if abnormal at screening or by decision of the treating team (not triplicate)

Ophthalmologic exam⁵: As outlined in section [6.1 Screening Assessments](#)

Radiologic assessment⁶: At screening and at the end of every cycle 6 cycles on treatment are mandatory.

Following radiologic assessments as per decision of local treating team

X⁷: Within 4 weeks (28 days) of screening

Optional Biologic Studies⁸: As outlined in section [6.1 Screening Assessments](#)

X⁹: All labs, physical exams, and vital signs, must be done within 14 days of starting Trametinib

X¹⁰: If applicable, dependent on treating team

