8.2.1 Radiographic Response

8.2.1.1 MRI/MRL:

MRI or MRL imaging will be recommended as primary imaging modality for all subjects enrolled in VATCH sub-protocols. For subjects with disease manifestation better characterized by alternative quantitative imaging modality (i.e. X-ray or ultrasound) this may be substituted and used as alternative imaging. MRI or MRL is the preferred method of imaging. MRI/MRL imaging will be done at screening and at the end of cycles 6, 12, and 24 on treatment. Additional assessments can be performed in accordance with the local institutional practice. For each imaging assessment timepoint initial radiographic response will be reviewed by each site's radiologist.

When possible and appropriate, volumetric imaging will be used in combination with standard vascular MRI protocols to assess vascular anomaly response. MRI will be performed using a 1.5 Tesla system (HDX 15.0 series MRI, GE and Espree B-15 series MRI, Siemens). Coronal and axial fast spin-echo T2-weighted sequences will be performed with and without fat suppression. Up to 3 lesions should be identified as target lesions and recorded and measured at screening. Target lesions should be selected on the basis of their size and their suitability for accurate repeated measurements (either by imaging techniques or clinically). The same method of assessment and the same technique should be used to characterize each target lesion at screening and during follow up ([APPENDIX VI](#)).

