8.2.2 Assessment of Patient Reported Outcome Measures (PROMs)

Quality of life is an essential component of high-quality clinical care.⁵³ The Patient Reported Outcomes Measurement Information System (PROMIS) is a validated parent/patient-reported scoring system that was developed with the National Institutes of Health (NIH) that can compare values across a variety of medical conditions.^{33,34} PROMIS is validated in individuals aged 8 years and older.⁵⁶⁻⁵⁸ A caregiver proxy report for the PROMIS measure is also available for use in children; for individuals younger than 8 years old, assessments must be completed by a caregiver proxy. PROMIS is considered to be the gold standard for HRQOL measurement in clinical trials. The recall timeframe for each question includes the past week.

Each question has five response categories. A raw score can be calculated for each PROMIS subscale. Raw scores are then translated into a T-score metric with mean of 50 (standard deviation of 10). A higher PROMIS T-score represents more of the concept being measured. Additional details for scoring and measure interpretation are available at <https://www.healthmeasures.net/score-and-interpret/interpret-scores/promis>. Higher scores represent better functioning. A difference or change in score of three points on the PROMIS Pediatric scale is considered a minimally important difference (MID).

In consultation with subjects, patient advocates, clinicians, and psychometricians, we will use global health measures as the **primary outcome** and pain interference as the **secondary outcome**. For exploratory outcomes, we will administer PROMIS measures for fatigue, anxiety, and depression. This survey battery will be administered every 6 cycles, starting at enrollment and continuing during participation in the study.

For subjects **18+ years old at enrollment**, please refer to “Adult subject 18+ y/o” column in [Table 8-3](#). In total, this battery of measures will include **26 items**. We will also include 2 open-ended questions for exploratory analysis: 1) What positive or negative changes have you noticed since you started taking the medication? 2) What else would you like us to know? For adults with cognitive impairment, guardian/LAR may provide proxy answers for the surveys at the discretion of the study chair and co-chair on a case-by-case basis.

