8.2.3 Assessment of Clinical Benefit

A set of clinical benefit assessments will supplement the radiographic and the PROMIS measures. The clinical benefit assessment tools will be determined at initial screening evaluation for the subject. The same clinical benefit assessment tools will be completed at enrollment and then every 6 cycles for the duration of the study. The investigator will determine the clinical benefit assessment and have this reviewed by the study PI if no radiologic assessment is noted. See [Appendix X](#).

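### Section 9.3 sets the short-term paired t-test at cycle 3, but imaging, PROMIS and CBA are first scheduled after baseline at the end of cycle 6

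*Protocol*

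**What the plan says.** Section 9.3 introduces secondary analyses of "longitudinal measurements of radiologic assessment, PROMIS Patient Reported Outcome measurements, and Clinical Benefit Assessments", which it says are "taken at screening, and at the end of cycles 6, 12, 18, and 24". It then specifies a paired t-test of change in these measures "from pre-treatment levels to the post-treatment level (follow-up at cycle 3"), with the stated purpose of evaluating short-term effects. It adds mixed effects models for change over time, and a signed rank test or a transformation if the data are not normal.

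The assessment schedules are given elsewhere in the protocol:

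- **Imaging.** Section 8.2.1.1: "MRI/MRL imaging will be done at screening and at the end of cycles 6, 12, and 24 on treatment". The Experimental Design Schema: "Radiologic assessment will occur at screening and the end of cycles 6, 12, and 24 (if applicable"). The radiology footnote to Table 8-1: "At screening and at the end of every cycle 6 cycles on treatment are mandatory", which we read as every 6 cycles.
- **PROMIS.** Section 8.2.2: "This survey battery will be administered every 6 cycles, starting at enrollment".
- **CBA.** Section 8.2.3: "The same clinical benefit assessment tools will be completed at enrollment and then every 6 cycles for the duration of the study".

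The synopsis gives the same pattern for all three.

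**The concern.** The paragraph fixes an analysis at a time that is missing from its own list of measurement times. The three measures are the components of the individualized response, and this comparison is the only one in 9.3 given both a specific time point and the aim of showing short-term effects.

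If the text stays as it is, the analyst has two choices. One is to use whatever unscheduled values happen to lie near cycle 3. The other is to choose a different time point once data are available. In a single-arm, open-label trial, that choice should be fixed in advance. An analysis plan that quietly used another time point would conflict with the protocol.

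**Working it through.** The plan attaches no figure to this test, so there is none to reproduce. The check compares the analysis time with the scheduled measurement times.

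**1. Scheduled times (in cycles, 0 = screening or enrollment)**

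| Measure | Scheduled times | Source | Cycle 3 included? |
|---|---|---|---|
| All three | 0, 6, 12, 18, 24 | Section 9.3 | No |
| Imaging | 0, 6, 12, 24 | Synopsis, Design Schema, Section 8.2.1.1 | No |
| Imaging | 0, then every 6 | Table 8-1, radiology footnote | No |
| PROMIS | 0, then every 6 | Synopsis, Design Schema, Section 8.2.2 | No |
| CBA | 0, then every 6 | Synopsis, Design Schema, Section 8.2.3 | No |

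Scheduled cycle 3 assessments: 0 of 3 measures, hence 0 of 39 planned evaluable subjects for each measure.

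**2. Could visit windows close the gap?** A cycle is 28 days. Section 8.1 allows ±3 days for cycles 1 to 3 and ±7 days afterwards.

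- End of cycle 3: 3 × 28 = day 84; window 84 ± 3 = days 81 to 87.
- End of cycle 6: 6 × 28 = day 168; window 168 ± 7 = days 161 to 175.
- Distance between the nominal days: 168 − 84 = 84 days, or 12 weeks.
- Distance between the nearest window edges: 161 − 87 = 74 days.

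Section 6 gives a general ±7 days. Applied to cycle 3, that makes days 77 to 91, still 161 − 91 = 70 days short. A cycle 6 value cannot count as a cycle 3 value.

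**3. What happens at cycle 3?** Section 6.1 sets an echocardiogram and an ECG at the end of cycle 3. A visit therefore exists, but these are safety assessments and not the measures in the t-test.

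**4. Where could early values come from?** There are three unscheduled routes: earlier assessment when there are signs of worsening (Design Schema), imaging at the treatment team's discretion (Design Schema), and additional imaging under local practice (Section 8.2.1.1). None is tied to cycle 3 or applies to all subjects.

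**5. First usable time.** All three measures are first scheduled together after baseline at the end of cycle 6. A paired test there would have scheduled data in up to 39 evaluable subjects. There would be fewer for imaging, which is done only where applicable, and fewer for PROMIS, which Section 6.1 does not use under 1 year of age.

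**The case against.** The strongest reply is that this is one mistaken time label on a secondary analysis with no alpha, power claim or decision rule attached. Section 9.3 already provides for analysing each follow-up visit separately and for mixed models across visits, so change at cycle 6 will be examined anyway. That is correct, and it limits the consequence to the named short-term test. A reader might infer that no test of change in the response components can be run; the paragraph does not support that.

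A reader might also infer that any early values must come from subjects who looked worse, so that the contrast is biased downward. The protocol does not support this either. Discretionary and local-practice imaging can be done for other reasons, and nothing in 9.3 says that unscheduled values would enter the test. What stands is that such values would be a selected subset, with bias of uncertain direction.

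Third, Section 8.1 makes Table 8-1 the full list of assessments, and its body is not readable here. A mark at cycle 3 cannot be ruled out. It would, however, contradict the radiology footnote for imaging, Sections 8.2.1.1, 8.2.2 and 8.2.3, and 9.3 itself, so the text would still need reconciling.

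Finally, the protocol does not show whether cycle 3 is a slip for cycle 6 or the remnant of an assessment since dropped. That affects the choice of repair, not whether one is needed.

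**Conclusion.** The contradiction is real and can be seen within a single paragraph of Section 9.3. The short-term paired t-test has no scheduled data for any of its three measures; the first scheduled post-baseline values come at the end of cycle 6 (week 24), 12 weeks after the named time.

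It would go too far to say that no cycle 3 values can exist: they are unscheduled, not impossible. Nor does the trial's main result depend on this. The primary endpoint is already assessed at the end of cycle 6, and the Simon two-stage rule and the toxicity monitoring do not use the test. The point should be corrected, but it is confined to one secondary analysis.

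The conclusion rests on the readable schedule statements and on the unread body of Table 8-1 agreeing with them.

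**What to change.** In Section 9.3, replace the parenthesis naming cycle 3 with the end of cycle 6, the first time at which all three measures are scheduled. Add one sentence saying that unscheduled early assessments do not enter this comparison. The cost is one phrase and one sentence, with no change to data collection. The downside is that the test then describes a 24-week rather than a 12-week effect.

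If a 12-week effect is what is wanted, the alternative is to add imaging, PROMIS and CBA at the end of cycle 3 to the schedule, which does add data collection.

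In the same edit, reconcile cycle 18 for imaging. Section 9.3 and the every-6-cycles footnote to Table 8-1 include it; the synopsis, the Design Schema and Section 8.2.1.1 schedule imaging only at cycles 6, 12 and 24.
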